### 9.3. Variables

This study will use data routinely captured in the ARTIS register, which include baseline patient characteristics (ie, demographic and clinical characteristics, comorbidities and current and past therapies, and safety events of special interest including serious infections, all malignancies, CVD events, and use during pregnancy. Infectious and cardiovascular events will be ascertained through record linkage with the Swedish Patient Register, which collects information on all hospitalised patients, and all visits to non-primary outpatient care. Diagnoses are assigned by the discharging/treating physician, as well as date of discharge/visit, hospital and department. Malignancies will be ascertained through linkage with the Swedish Cancer Register which contains data on date of cancer diagnosis and type of cancer according to the International Classification of Disease (ICD). classification. Use in pregnancy will be assessed through additional linkage with the Medical Birth Register which contains data from antenatal, obstetric, and neonatal records, and covers all live and still births (but not all miscarriages) in Sweden.

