#### **Rationale and background:**

Rituximab is a genetically engineered chimeric mouse/human monoclonal IgG1k antibody targeting the transmembrane CD20 antigen. CD20 is a 32-kDa, non-glycosylated transmembrane phosphoprotein, located on the surface of normal precursor-B cells, mature B lymphocytes and malignant B cells. The natural ligand for CD20 has not been identified, and the biological function of CD20 remains unclear. Rituximab binds to a discontinuous conformational epitope on CD20 and initiates multiple immune effector functions leading to target cell lysis. The currently approved indications for licensed rituximab (MabThera) are for Rheumatoid arthritis (RA), Non-Hodgkin's lymphoma (NHL), Chronic lymphocytic leukaemia (CLL), Granulomatosis with polyangiitis (GPA), Microscopic polyangiitis (MPA) and Pemphigus vulgaris (PV).

Licensed as MabThera in the European Union (EU) in 1998, rituximab was the first biologic on the market for RA for specific B cell targeting therapy. Rituximab in combination with methotrexate is indicated for the treatment of adult patients with severe active RA who have had an inadequate response or intolerance to other disease-modifying antirheumatic drugs (DMARDs) including one or more tumour necrosis factor (TNF) inhibitor therapies. Approved in the EU on 01 April 2020, PF-05280586 (Ruxience) has been developed by Pfizer as a biosimilar to the licensed reference product, MabThera. Pfizer proposes the assessment of safety events of special interest based on the Ruxience EU Risk Management Plan (RMP) version 1.0 (infections including serious infections (Important Identified Risk), malignancies (Important Potential Risk), impact on cardiovascular disease (CVD) (Important Potential Risk) and use in pregnancy (Missing Information)). This protocol describes a non-interventional, Post-Authorisation Safety Study (PASS) of Ruxience-exposed patients using actively collected prospective data included in the established Anti-Rheumatic Therapies in Sweden (ARTIS) register.

**Research question:** What are the incidence rates of safety events of special interest in patients with RA who initiate Ruxience in the ARTIS register?

**Objectives:** To estimate incidence rates of infections, including serious infections, malignancies, cardiovascular events, and use during pregnancy among all patients with rheumatoid arthritis in the ARTIS register who initiate Ruxience.

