### Objectives:

To estimate incidence rates of infections, including serious infections, malignancies, cardiovascular events, and use during pregnancy among RA patients in the ARTIS register who initiate treatment with Ruxience.

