### 9.3.3. Endpoints of Interest

For the interim and final safety reports (which will include information on patients, covariates and incidence rates for pre-specified safety outcomes, from SRQ as well as from the linked Patient/Prescribed Drug and other registers), the following events of interest have been pre-specified.

1. Hospitalised infections overall.
2. NMSC.
3. Malignancies, excluding NMSC.
4. CV events, including but not limited to deep vein thrombosis/pulmonary embolism.
5. Use during pregnancy.

In addition, the final study report will include the number of Ruxience-exposed pregnancies. If data are sufficient, rates of diagnosed malformations can be provided however, the number of Ruxience-exposed pregnancies is expected to be low based on previous data for other biosimilars.

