### 9.7.2. Interim and Final Study Reports

The interim and final reports will present data on safety events of interest identified through linkages with the patient, cancer, and death registers as appropriate.

For these analyses, the Ruxience cohort will be analysed overall and stratified by previous biologics use. The general analytic approach will be descriptive and include incidence rates of events of interest within the Ruxience cohort. Incidence rates will be calculated by dividing the number of events by the person-time of exposure and will include 95% confidence intervals.

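### Exposed pregnancies are to be counted from a birth register that misses some losses, and any pregnancy rate would be diluted by person-time of patients who cannot become pregnant

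*Protocol*

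**What the plan says.** Section 9.3 gives the source: "Use in pregnancy will be assessed through additional linkage with the Medical Birth Register". The same section, and again Section 9.4.5, describes that register's coverage: it "covers all live and still births (but not all miscarriages) in Sweden". The Patient Register is given a different task: "Infectious and cardiovascular events will be ascertained through record linkage with the Swedish Patient Register". Section 9.2.3 limits the study to health outcomes from national registers, so the spontaneous reports that ARTIS also holds are not a second source.

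Three outputs are planned for pregnancy:

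- **A count.** Section 9.3.3 says that "the final study report will include the number of Ruxience-exposed pregnancies".
- **A rate.** Use during pregnancy is item 5 among the pre-specified events. The objective in Section 8 asks for incidence rates of several events, including "use during pregnancy among RA patients in the ARTIS register who initiate treatment with Ruxience". The abstract's version reads "use during pregnancy among all patients with rheumatoid arthritis in the ARTIS register who initiate Ruxience".
- **Malformation rates**, only if the data suffice (Section 9.3.3).

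Section 9.7.2 gives one formula for all events: "Incidence rates will be calculated by dividing the number of events by the person-time of exposure and will include 95% confidence intervals". It says that the events are "identified through linkages with the patient, cancer, and death registers as appropriate". Section 9.2.1 admits adults with RA who start Ruxience, with no restriction by sex and no upper age limit, and Section 9.2.2 excludes nobody.

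**The concern.** Whether a pregnancy enters a birth register depends on how it ended. A pregnancy that reaches a live or still birth is recorded, and one that ends earlier may not be. The shortfall is therefore not random: the pregnancies missed are losses. A reader of the final report would take the number of exposed pregnancies at face value, although it is closer to the number that reached a registered birth. A malformation rate built on the same records would leave out an affected pregnancy that ended earlier and was not registered.

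The second issue is the denominator. Men and women past childbearing age contribute person-time but cannot contribute an event. A rate over the whole cohort then reflects its age and sex mix as much as the frequency of exposure in pregnancy.

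Use in pregnancy is a named objective, listed in the RMP as missing information (Section 7). Section 9.3.3 expects few exposed pregnancies, so each one missed weighs more.

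**Working it through.** **No figure to reproduce.** The protocol gives no expected count, rate, denominator or precision for pregnancy, and Table 2 has no pregnancy row. The rows that Table 2 does have reproduce with exact (Clopper-Pearson) limits on 73 patients: 22 events give 0.199 to 0.420, 3 give 0.009 to 0.115, 1 gives 0.000 to 0.074, and 0 give 0.000 to 0.049. They do not bear on this point.

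**Source against promised output.** Section 9.3 names one register for pregnancy and describes its coverage of miscarriages as incomplete. Section 9.3.3 promises the number of exposed pregnancies with no such limit. Section 9.9 (limitations) discusses endpoint misclassification, channelling, the absence of controls and the length of follow-up, but not pregnancy capture. The gap is disclosed where the register is described and is not carried to the endpoint or the limitations.

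**Size of the undercount, on assumptions.** Let L be the share of exposed pregnancies ending in miscarriage or termination, and c the share of those losses that the birth register sees. Neither value is in the documents.

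- Share of exposed pregnancies seen = (1 − L) + L × c
- Apparent share of losses among those seen = L × c / [(1 − L) + L × c]

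| L | c = 0: seen / apparent losses | c = 0.25 | c = 0.5 |
|---|---|---|---|
| 10% | 90% / 0% | 92.5% / 2.7% | 95% / 5.3% |
| 20% | 80% / 0% | 85% / 5.9% | 90% / 11.1% |
| 30% | 70% / 0% | 77.5% / 9.7% | 85% / 17.6% |
| 40% | 60% / 0% | 70% / 14.3% | 80% / 25.0% |

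For example, with L = 20% and c = 0.25, the share seen is 0.80 + 0.05 = 0.85. Losses appear as 0.05 / 0.85 = 5.9% instead of 20%. The direction is the same whenever L is above 0 and c is below 1.

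**Size of the dilution, on an assumption.** Let f be the share of person-time held by women of childbearing age, also not in the documents. All events arise in that share, so:

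- Rate over all patients = f × rate among women of childbearing age
- Factor by which the rate is lowered = 1 / f

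For f = 5%, 10%, 20% and 30%, the factor is 20, 10, 5 and 3.3.

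**Is a remedy within reach?** Sections 9.3 and 9.4.3 say that the Patient Register holds all hospitalisations and all non-primary outpatient visits, with diagnoses in ICD-10 since 1997. It is already linked. Section 9.3.1 lists age and sex among the captured data. Neither change needs a new data source.

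**The case against.** **Disclosure.** The protocol states the miscarriage gap in the abstract and in Sections 9.3 and 9.4.5. That is correct, and nothing is hidden. The disclosure does not alter the unqualified count in Section 9.3.3, and Section 9.9 does not repeat it.

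**Not stated to be the only source.** Section 9.3 calls the birth register linkage additional. Section 9.3.3 says that the reports draw on SRQ and on the linked Patient, Prescribed Drug and other registers. Nothing forbids Patient Register codes for pregnancy. But Section 9.3 assigns that register to infections and cardiovascular events, and no passage assigns it to pregnancy.

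**The denominator belongs to the analysis plan.** The abstract's reference to all patients stands in a sentence covering every event, and the objective in Section 8 omits the word. The formula in Section 9.7.2 is generic. The main pregnancy output is a count, which needs no denominator. All of this stands and makes the denominator the weaker half of the point. It remains that the protocol lists pregnancy among events with incidence rates and gives only an unrestricted formula.

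**Stronger readings that the text does not support.**

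- A reader might infer that many miscarriages are missing. The text says only that not all are covered, which implies that some are.
- A reader might take it as stated that terminations are absent. The documents never mention them; their absence is a fair inference from the coverage description.
- A reader might conclude that only good outcomes are seen. Still births are covered, so the tilt is toward births.
- A reader might call the all-patient rate meaningless. It is defined, but diluted and hard to interpret.
- A reader might conclude from Section 9.7.2 that the birth register will not be used. That list is qualified and leaves out other registers too, so this is a slip of wording.

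**Chance may dominate.** With few exposed pregnancies, random error may exceed either effect. That is possible, but it does not remove an error of known direction that is cheap to reduce.

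**Conclusion.** The point holds in a limited form. If Section 9.3 is followed as written, the number of exposed pregnancies promised in Section 9.3.3 will be too low and pregnancy losses under-represented. This rests on two conditions: some exposed pregnancies end in loss, and the birth register does not record all of those. The protocol itself says the second of miscarriages.

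The amount cannot be fixed from the documents. The 60% to 95% capture range illustrates assumed values of L and c and is not an estimate for this cohort. The 3.3-fold to 20-fold dilution rests on an assumed f and applies only if a rate is reported over the whole cohort's person-time. The count is unaffected by the denominator but keeps the undercount. The change is worth making because pregnancy is a stated objective and the data needed are already in the linkage.

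**What to change.** - **Sections 9.3 and 9.3.3:** add pregnancies with loss or termination diagnoses (ICD-10 O00-O08) from the Patient Register. Report them separately from pregnancies ending in a registered live or still birth, and state the remaining undercount.
- **Section 9.9:** add incomplete pregnancy capture to the limitations.
- **Section 9.7.2:** name the Medical Birth Register among the linkages. If a pregnancy rate is reported, use only the person-time of women of childbearing age.

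The cost is one more code list, some programming and a few sentences. Losses not seen in hospital or specialist care would remain uncaptured, which is why the undercount must still be stated.

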#### 9.3.1. Baseline Data

The data captured include, but are not restricted to, the following: age, sex, years since diagnosis, disease severity, drug history, comorbidities (eg, history of malignancies), current concomitant medications, etc.

#### 9.3.2. Follow-Up and Risk Window

Patients will be followed from treatment start (Index Date) until each outcome of interest, death, emigration from Sweden and end of study follow-up treated as censoring events. The Study End Date is defined as 3 years after the Study Start Date (date when first patient diagnosed with RA in ARTIS initiates treatment with Ruxience).

Some outcomes of interest in this study are thought to potentially occur at a higher rate while on drug, but that increased risk subsides after the drug is discontinued (ie, serious infections, CV events). Those events will be evaluated over a risk window that includes time from drug initiation until 270 days (eg, 9 months) after end of treatment (ie, last dose of Ruxience). The 270-day extension period is implemented to accommodate the very long half-life of Ruxience, and to ensure that any subclinical or undiagnosed illness at time of end of treatment is captured. For non-melanoma skin cancer (NMSC) and other malignancies, the manifestation of which is expected to be delayed relative to the time of exposure, the outcomes will be evaluated from drug initiation until the first event or loss to follow up, reflecting a once-exposed always at-risk paradigm.

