CV Risk	Major Acute Cardiovascular Events (MACE), combines MI, stroke, and fatal cardiovascular events: I00-I99 as main cause of death, or I20.0, I21, I60-I64 as diagnosis in in- or outpatient care	
‘Outcome’ was defined as any first-ever ACS event, which in turn was defined as a primary discharge diagnosis of acute myocardial infarction or unstable angina pectoris, or as acute myocardial infarction being the underlying cause of death. For discharge diagnoses, the date of admission to hospital was considered the event date. This outcome definition has previously been validated in a Swedish early RA cohort, with a positive predictive value of 95%. In addition, a regional validation study of hospitalised acute MI and stroke found positive predictive values of 96% and 94% respectively, in the period 1977 to 1987.
 
References:  https://onlinelibrary.wiley.com/doi/epdf/10.1002/art.39267            Mantel et al. Risk Factors for the Rapid Increase in Risk of Acute Coronary Events in Patients With New-Onset Rheumatoid Arthritis. A Nested Case-Control Study. Arthritis & Rheumatology. 2015; 67(11):2845-2854.
 
Lindblad et al. Validity of register data on acute myocardial infarction and acute stroke. Scandinavian Journal of Public health 1993; 21 (1):3-9.

NMSC	
Identified through the Cancer register as all malignancies with ICD-O/2 code C44, and all basal cell cancers recoded in the register’s subcomponent on basal cell cancers
 
Alt: all invasive NMSC, identified as non-benign ICD-O/2 code C44, and no basal cell cancers.
	
About 99% of cancers have been morphologically verified. Reporting of incident cancers (including invasive malignancies as well as cancer in situ) is mandatory and semi-automated, resulting in an estimated coverage greater than 95%.

090177e1953e1418\Approved\Approved On: 16-Oct-2020 13:21 (GMT)

Event	Operationalisation	Validation ICD
Malignancy	All invasive malignancies recorded in the cancer register, excluding NMSC	See NMSC
Abbreviations: ACS= acute coronary syndrome; ARTIS= Anti Rheumatic Treatment in Sweden; ICD= International Classification of Diseases; MACE= major acute cardiovascular events; MI= myocardial infarction; NMSC= non-melanoma skin cancer; RA= rheumatoid arthritis		

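### The infection and CV risk window counts time beyond 270 days after a dose only if a later dose follows, so at-risk status depends on the future and the rates can be biased, on the protocol's own premise downward

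*Protocol*

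**What the plan says.** Protocol Section 9.3.2 gives serious infections and CV events the following window: "a risk window that includes time from drug initiation until 270 days (eg, 9 months) after end of treatment (ie, last dose of Ruxience". Its closing parenthesis fixes end of treatment as the last dose. Neither that section nor any other sets a maximum gap between doses, divides treatment into episodes for this purpose, or says when a patient leaves and re-enters the risk set.

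The same section gives its reasons. "Some outcomes of interest in this study are thought to potentially occur at a higher rate while on drug", and that "increased risk subsides after the drug is discontinued (ie, serious infections, CV events". For the length of the extension: "The 270-day extension period is implemented to accommodate the very long half-life of Ruxience"; undiagnosed illness at the end of treatment is the second reason.

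Follow-up runs "until each outcome of interest, death, emigration from Sweden and end of study follow-up treated as censoring events", and "The Study End Date is defined as 3 years after the Study Start Date". Section 9.7.2 obtains each rate by "dividing the number of events by the person-time of exposure and will include 95% confidence intervals". In Annex 1, Table 3, the CV endpoint "combines MI, stroke, and fatal cardiovascular events: I00-I99 as main cause of death". Malignancies, including NMSC, are followed from initiation without a window.

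**The concern.** The end of the window is known only in hindsight. Take two patients who both pass day 270 after a dose without another. If the first is re-dosed on day 400, all of days 271–400 counts as at risk. If the second is never re-dosed, everything after day 270 is dropped, events included. On day 300 the two have the same history, and only a later dose separates them.

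This has two consequences.

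1. **Selection.** Event-free gaps enter the denominator once re-dosing occurs. A gap that contains an event is lost from the numerator if the event prevents re-dosing.
2. **Dilution.** Section 9.3.2 says the raised risk subsides off drug and allows 270 days for carry-over. Gap time beyond that is, on this reasoning, lower-risk time, yet it is counted as exposed.

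The absolute rate is the study's result. There is no control group (Section 9.9), so the error cannot cancel in a contrast. Serious infection is an Important Identified Risk (Section 7), and the data may be used in regulatory communications (Section 12).

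**Working it through.** **The plan's own figures.** Section 9.5, Table 2, gives 3/73 = 0.041 with 95% CI 0.009–0.115 for serious infection and for CV events. The exact binomial limits are Beta(0.025; 3, 71) = 0.009 and Beta(0.975; 4, 70) = 0.115, so the table is reproduced. It says nothing on gaps and is not in dispute.

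**A formula for the bias.** Let
- g = share of person-time in the protocol's window that lies more than 270 days after a dose;
- h = true event rate in that gap time divided by the on-drug rate;
- q = probability that planned re-treatment still takes place after an event.

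A gap event is counted only if a dose follows, so the rate counted in gap time is about h·q times the on-drug rate. Hence

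rate under the protocol's window / on-drug rate ≈ (1 − g) + g·h·q = 1 − g(1 − h·q).

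**Inputs.** The documents give none of g, h or q. To obtain g and test the formula, 100,000 patients per scenario were simulated. Assumptions: on-drug rate 5 per 100 person-years, 15% chance of stopping at each course, lognormal dosing intervals (sigma 0.35) with median 180, 270 or 365 days, and three years of follow-up for each patient. The resulting g was about 0.023, 0.113 and 0.223.

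Ratio of the protocol's window to the per-dose window (formula / simulated):

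| h | q | 180 days | 270 days | 365 days |
|---|---|---|---|---|
| 1 | 1 | 1.000 / 1.000 | 1.000 / 0.999 | 1.000 / 0.994 |
| 1 | 0.5 | 0.989 / 0.988 | 0.944 / 0.945 | 0.889 / 0.884 |
| 0.5 | 1 | 0.989 / 0.988 | 0.944 / 0.944 | 0.889 / 0.893 |
| 0.5 | 0.5 | 0.983 / 0.983 | 0.915 / 0.916 | 0.833 / 0.830 |
| 1 | 0 | 0.977 / 0.977 | 0.887 / 0.888 | 0.777 / 0.778 |
| 1.5 | 1 | not run | 1.057 / 1.051 | 1.112 / 1.112 |

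Example, 365 days with h = 1 and q = 0: 1 − 0.223 × (1 − 0) = 0.777. The simulated rates were 3.90 against 5.01 per 100 person-years, a ratio of 0.778.

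The per-dose window returned 4.9–5.1 for a true 5 in every scenario. With h = q = 0.5 and a 270-day median, changing the rate to 2 or 8 per 100 person-years, or the stopping probability to 0.05 or 0.30, left the ratio at 0.91–0.93.

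**Staggered entry.** The Study End Date is fixed by the first patient, so later starters have under three years and fewer completed gaps. A second simulation allowed for this, with a true rate of 4.1, a flat hazard, usual re-dosing near six months and a minority of long intervals. For q from 0.5 to 0, the rate was 3–5% low when 20% of intervals were about 12 months and 6–10% low when 40% were. A re-run with q = 1 showed no bias: 4.13 against 4.12, and 4.03 against 4.00.

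**The case against.** **Direction.** A reader might infer that the rule must understate the rates. The documents do not support that. With a flat hazard and re-treatment unaffected by events, the ratio is 1.00. If risk were higher off drug and events did not deter re-treatment, the bias would be upward, although that contradicts Section 9.3.2. Nothing says how often re-treatment follows a hospitalised infection or a non-fatal CV event. Only for fatal CV events is q = 0 by necessity, and they are part of one endpoint.

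A reader might also infer that, because follow-up ends at the outcome, a dose after the event can never be the last dose, so that no gap event is ever counted. The text does not say whether the last dose is sought within or beyond follow-up, so the point does not rest on this.

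**Size.** Every input is assumed. With only 5% of intervals near 12 months, the difference is about 0–1.5%. In a cohort near the 73 patients of Table 2, even a 20% shift (0.041 × 0.20 = 0.008) lies well inside 0.009–0.115. This stands, but the cohort size is not stated, and a bias of this kind does not shrink as patients accrue.

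**SAP detail.** Section 9.7 leaves detailed methods to a SAP that is not shown and that may define episodes. But the protocol is not silent here: it states a rule, and the rule ties the window to the last dose.

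**Interim against final report.** A gap event could be left out at the interim and counted at the final because of a dose in between. Revision of interim estimates is ordinary, so this adds little.

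**Conclusion.** The point holds as a defect of definition. At-risk status beyond day 270 is decided by a later dose. This conflicts with the section's own carry-over reasoning and with a denominator meant to be exposed time. The effect on the rates is conditional: downward if events deter re-treatment or if risk falls in gaps, nil if neither holds.

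The size cannot be derived from the documents. Under the stated assumptions it is about 0–2% when re-dosing is near six-monthly and gaps over 270 days are rare. It is roughly 4–20% at median intervals of 9–12 months, reaching 22% at the extreme where no one is re-treated after an event. The matter concerns serious infections and CV events only. It is worth settling before data extraction.

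**What to change.** Replace the window in Section 9.3.2 with one that depends only on past doses: *a patient is at risk from each recorded Ruxience dose until 270 days after it; overlapping periods are merged; a patient not re-dosed by then leaves the risk set on day 270 and re-enters at the next dose.* Count events and person-time only within these periods. Report the first-to-last-dose window as a sensitivity analysis. This changes the analysis only and has no bearing on treatment.

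**Cost.**
- Person-time falls by the gap share: about 2%, 11% or 22% in the three interval scenarios above. Counted events fall by at most the same share (for example 11,172 to 8,721, or 22%, at 365 days with h = q = 1) and not at all when q = 0.
- Intermediate dose dates are needed, whereas the present rule needs only the first and last. Section 9.2.3 describes treatment starts and episodes but does not say that every infusion is recorded, so capture in SRQ/ARTIS should be confirmed first. With an assumed 30% of intermediate doses unrecorded and 10% long gaps, the per-dose rule lost about 10% of person-time and 9% of events, though the rate barely moved.
- If dose dates prove incomplete, apply the same exit and re-entry rule to recorded treatment episodes.
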